10.3. Statistical Analyses

10.3.1. Safety Analyses

All safety analyses will be performed on the Safety Population.

Endpoint	Statistical Analysis Methods
Primary and Secondary	
No formal statistical testing will be performed on safety data.
 
If deemed appropriate posterior probabilities of the true rate of an adverse event of interest may be calculated using a non-informative prior distribution.
 
Clinical interpretation will be based upon review and displays of adverse events, disease related events, laboratory values and vital signs. The principal consideration in this evaluation will be the investigator-reported relationships of either adverse events or laboratory abnormalities to investigational product.
 
Safety data including immunogenicity data will be presented in tabular and/or graphical format and summarized descriptively according to GSK's Integrated Data Standards Library (IDSL) standard.
 
Target Engagement will be presented in tabular and graphical format and summarized descriptively according to GSK's IDSL standard for Pharmacodynamic endpoints.
 
Sparse blood sampling is being implemented in this study to allow the full pharmacokinetic profile for each participant to be reconstructed using Bayesian prediction from a population pharmacokinetic model using Non Linear Mixed Effect Model (NONMEM) version VII or higher and determine the exposure over the dosing interval (AUC (0- τ)), apparent systemic clearance (CL/F), and apparent volume of distribution (Vss/F).
 
Plasma GSK2330811 concentration data will be presented in tabular and graphical format and summarized descriptively according to GSK's IDSL standards.

Exploratory	Will be described in the reporting and analysis plan (RAP).

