
 • Any abnormal laboratory test results (hematology, clinical chemistry, or urinalysis) or other safety assessments (eg, ECG, radiological scans, vital signs measurements), including those that worsen from baseline, considered clinically significant in the medical and scientific judgment of the investigator (ie, not related to progression of underlying disease). • Exacerbation of a chronic or intermittent pre-existing condition including either an increase in frequency and/or intensity of the condition. • New conditions detected or diagnosed after study treatment administration even though it may have been present before the start of the study. • Signs, symptoms, or the clinical sequelae of a suspected drug-drug interaction. • Signs, symptoms, or the clinical sequelae of a suspected overdose of either study treatment or a concomitant medication. Overdose per se will not be reported as an AE/SAE unless it is an intentional overdose taken with possible suicidal/self-harming intent. Such overdoses should be reported regardless of sequelae. • "Lack of efficacy" or "failure of expected pharmacological action" per se will not be reported as an AE or SAE. Such instances will be captured in the efficacy assessments. However, the signs, symptoms, and/or clinical sequelae resulting from lack of efficacy will be reported as AE or SAE if they fulfill the definition of an AE or SAE. • The signs, symptoms, and/or clinical sequelae resulting from lack of efficacy will be reported as AE or SAE if they fulfill the definition of an AE or SAE. Also, "lack of efficacy" or "failure of expected pharmacological action" constitutes an AE or SAE.

Events NOT Meeting the AE Definition

- Any clinically significant abnormal laboratory findings or other abnormal safety assessments which are associated with the underlying disease, unless judged by the investigator to be more severe than expected for the participant's condition.
- The disease/disorder being studied or expected progression, signs, or symptoms of the disease/disorder being studied, unless more severe than expected for the participant's condition.
- Medical or surgical procedure (eg, endoscopy, appendectomy): the condition that leads to the procedure is the AE.
- Situations in which an untoward medical occurrence did not occur (social and/or convenience admission to a hospital).

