- Anticipated day-to-day fluctuations of pre-existing disease(s) or condition(s) present or detected at the start of the study that do not worsen.

Definition of SAE

If an event is not an AE per definition above, then it cannot be an SAE even if serious conditions are met (eg, hospitalization for signs/symptoms of the disease under study, death due to progression of disease).

A SAE is defined as any untoward medical occurrence that, at any dose:

a. Results in death

b. Is life-threatening

The term 'life-threatening' in the definition of 'serious' refers to an event in which the participant was at risk of death at the time of the event. It does not refer to an event, which hypothetically might have caused death, if it were more severe.

c. Requires inpatient hospitalization or prolongation of existing hospitalization

In general, hospitalization signifies that the participant has been detained (usually involving at least an overnight stay) at the hospital or emergency ward for observation and/or treatment that would not have been appropriate in the physician's office or outpatient setting. Complications that occur during hospitalization are AE. If a complication prolongs hospitalization or fulfills any other serious criteria, the event is serious. When in doubt as to whether "hospitalization" occurred or was necessary, the AE should be considered serious.

Hospitalization for elective treatment of a pre-existing condition that did not worsen from baseline is not considered an AE.

d. Results in persistent disability/incapacity

- The term disability means a substantial disruption of a person's ability to conduct

normal life functions.
 
 This definition is not intended to include experiences of relatively minor medical significance such as uncomplicated headache, nausea, vomiting, diarrhea, influenza, and accidental trauma (eg, sprained ankle) which may interfere with or prevent everyday life functions but do not constitute a substantial disruption.

e. Is a congenital anomaly/birth defect

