16. APPENDICES

16.1. Appendix 1: Protocol Deviation Management and Definitions for Per Protocol Population

16.1.1. Exclusions from Per Protocol Population

A participant meeting any of the following criteria will be excluded from the Per Protocol population:

Number	Exclusion Description		
01	Participant did not receive at least 4 doses of study treatment		
02	Placebo participant received active treatment		
03	Participant did not participate in at least one post-dose assessment		
04 ^[1]	Participant excluded on basis of final review of inclusion/exclusion criteria		
05 ^[1]	Participant excluded on basis of final review of the prohibited medication use		
^[1] Note: Da	^[1] Note: Data reviewed and decisions regarding exclusions from the Per Protocol population will be		

201247

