16.12.18. Exploratory Efficacy Tables

Exploratory Efficacy: Tables						
No.	Population	IDSL / Example Shell	Title	Programming Notes	Deliverable [Priority]	
mRSS						
9.1	Per Protocol	EFF_T1	Summary of mRSS Total Score	By treatment, by visit	SAC	
9.2	Per Protocol	EFF_T1	Summary of Change from Baseline in mRSS Total Score	By treatment, by visit	SAC	
9.3	Per Protocol	EFF_T2	Analysis of Change from Baseline in mRSS Total Score	By treatment, by visit	SAC	
FVC and	% predicted F	VC				
9.4	Per Protocol	EFF_T1	Summary of Laboratory FVC (L)	By treatment, by visit	SAC	
9.5	Per Protocol	EFF_T1	Summary of Change from Baseline in Laboratory FVC (L)	By treatment, by visit	SAC	
9.6	Per Protocol	EFF_T2	Analysis of Change from Baseline in Laboratory FVC (L)	By treatment, by visit	SAC	
9.7	Per Protocol	EFF_T1	Summary of Laboratory Percent Predicted FVC	By treatment, by visit	SAC	
9.8	Per Protocol	EFF_T1	Summary of Change from Baseline in Laboratory Percent Predicted FVC	By treatment, by visit	SAC	
HAQ-DI a	nd SHAQ VAS	scales				
9.9	Per Protocol	EFF_T1	Summary of HAQ-DI	By treatment, by visit	SAC	
9.10	Per Protocol	EFF_T1	Summary of Change from Baseline in HAQ-DI	By treatment, by visit	SAC	
9.11	Per Protocol	EFF_T2	Analysis of Change from Baseline in HAQ-DI	By treatment, by visit	SAC	
9.12	Per Protocol	EFF_T1	Summary of SHAQ VAS scales	By treatment, by visit, by VAS scale	SAC	
9.13	Per Protocol	EFF_T1	Summary of Change from Baseline in SHAQ VAS scales	Add footnote: "Note: US English version of SHAQ-VAS Questionnaire presented in the output."	SAC	
PhGA and	d PtGA					
9.14	Per Protocol	EFF_T1	Summary of Physician Assessment of Global Disease Activity	By treatment, by visit	SAC	

Exploratory Efficacy: Tables							
No.	Population	IDSL / Example Shell	Title	Programming Notes	Deliverable [Priority]		
9.15	Per Protocol	EFF_T1	Summary of Change from Baseline in Physician Assessment of Global Disease Activity	By treatment, by visit	SAC		
9.16	Per Protocol	EFF_T1	Summary of Patient Assessment of Global Disease Activity	By treatment, by visit	SAC		
9.17	Per Protocol	EFF_T1	Summary of Change from Baseline in Patient Assessment of Global Disease Activity	By treatment, by visit	SAC		
CRISS							
9.18	Per Protocol	EFF_T4	Summary of CRISS	Per visit (i.e. 12 weeks and follow up), by treatment. Use non-parametric summaries only	SAC		
9.19	Per Protocol	EFF_T5	Summary of CRISS Step 1 Events		SAC		
9.20	Per Protocol	EFF_T6	Analysis of CRISS		SAC		
Home FV	Home FVC						

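### The protocol promises a Safety Population display of disease related events, but the SAP has none, and its only count of SSc organ events (Table 9.19) is on the Per Protocol population

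*Protocol*

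**What the plan says.** Protocol section 10.3.1 names four inputs to the safety interpretation: "Clinical interpretation will be based upon review and displays of adverse events, disease related events, laboratory values and vital signs". It also fixes the population: "All safety analyses will be performed on the Safety Population". Neither the protocol nor the SAP defines a disease related event.

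Protocol Appendix 4 (section 12.4) lists among events that are not AEs: "The disease/disorder being studied or expected progression, signs, or symptoms of the disease/disorder being studied, unless more severe than expected". It then closes the SAE route for such events: "If an event is not an AE per definition above, then it cannot be an SAE even if serious conditions are met". Its examples are "hospitalization for signs/symptoms of the disease under study, death due to progression of disease". The same appendix counts this as an AE: "New conditions detected or diagnosed after study treatment administration even though it may have been present before the start of the study". It does the same for an exacerbation of a pre-existing condition.

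SAP section 7 and Tables 3.1 to 3.36 cover adverse events, laboratory data, ECG, vital signs and immunogenicity. SSc organ events are tabulated once, in Table 9.19, "Summary of CRISS Step 1 Events", on the Per Protocol population. SAP section 16.6.3 gives its four items: renal crisis, FVC decline with interstitial lung disease, left ventricular failure and pulmonary arterial hypertension (PAH). SAP section 16.1.1 excludes from Per Protocol anyone with fewer than 4 doses, and also: "Participant excluded on basis of final review of the prohibited medication use".

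**The concern.** Safety is the primary objective, and worsening of SSc is a possible harm of a mechanism not previously tested in this disease. The protocol's answer is to display disease related events beside adverse events. The SAP drops that display without saying so.

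The one table that could stand in for it uses a population selected on events after randomisation. Under protocol sections 7.7.2 and 8.1.1, starting a prohibited drug during the treatment period ends study treatment for good. Most of the prohibitions run to Day 197, so a participant who received all six doses could also be excluded on final review for use during follow-up. People whose disease is worsening are plausibly over-represented among those excluded. A safety display should not be conditioned on that.

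**Working it through.** **Where an SSc organ event would be counted.** Two conditions decide it.

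| | Participant in Per Protocol | Participant excluded from Per Protocol |
|---|---|---|
| Reported as an AE or SAE | AE/SAE tables (such as 3.1, 3.9) and Table 9.19 | AE/SAE tables |
| Judged expected progression, so not an AE | Table 9.19 | Neither |

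Only the lower right cell is lost. Reaching it needs an organ event, a judgement that it was expected progression, and exclusion from Per Protocol (fewer than 4 of the 6 doses, or prohibited medication after review).

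**Whether the omission was decided.** SAP Table 1 lists two changes from the protocol's analysis: adding PD data to the cohort 1 review, and splitting the enrolled population. Neither concerns disease related events, so this reads as an oversight.

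**Whether the data exist.** Participants who stop treatment are to continue visits (protocol sections 8.1 and 8.1.1). SAP section 16.6.3 says renal crisis, ventricular failure and PAH are captured in the eCRF; the FVC criterion is derived by program. Protocol section 9.2.5 requires the Death form for every death, SAE or not. The schedule of activities has CRISS data at Days 1, 85 and 197 only, with no entry at Early Withdrawal.

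**The plan's own figures.** Protocol Table 3 uses a Beta(1,1) prior. The upper limit is the 97.5th percentile of Beta(1 + x, 1 + n − x), for x events in n participants. For n = 15:

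| x | Recomputed | Table 3 |
|---|---|---|
| 0 | 0.2059 | 0.206 |
| 1 | 0.3023 | 0.302 |
| 2 | 0.3835 | 0.383 |
| 3 | 0.4565 | 0.456 |

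The four limits for n = 3 also reproduce. No stated figure is disputed.

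**Illustration.** The documents give no count of uncounted events, so I assume 0 to 3 among 15 active participants, each excluded from Per Protocol. With 0 nothing changes. For x = 0 the limit is 1 − 0.025^(1/(n + 1)); at n = 14 this is 1 − 0.025^(1/15) = 0.218.

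| Uncounted events | Per Protocol view | Upper limit | Safety Population | Upper limit |
|---|---|---|---|---|
| 1 | 0/14 | 0.218 | 1/15 | 0.302 |
| 2 | 0/13 | 0.232 | 2/15 | 0.383 |
| 3 | 0/12 | 0.247 | 3/15 | 0.456 |

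One event is 1/15 = 6.7 percentage points at the minimum size of cohort 2. At the maximum of 36 participants, 3:1 allocation gives 27 on active treatment, and one event is 1/27 = 3.7 points.

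**The case against.** A reader might infer that organ crises in anyone who stopped treatment early vanish from every summary. The documents do not support that.

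- Stopping early removes no one by itself. A participant who stops after dose 4 or 5 stays in Per Protocol unless another exclusion applies, and the prohibited-medication exclusion follows a review.
- Appendix 4 brings many organ events back in. Progression that is worse than expected is an AE, and so are new conditions. Three of the four CRISS Step 1 items are worded as new events. Heart failure, arrhythmias and pulmonary hypertension have their own cardiovascular CRF page. Events reported this way enter the AE/SAE tables on the Safety Population.
- Other Safety displays would carry traces: reasons for stopping treatment (Table 1.3), Per Protocol exclusions (1.9), concomitant medication (1.27), worst-case chemistry (3.18) and vital sign limits (3.35). HRCT and arrhythmia listings use the Enrolled population. ICH listings 1 to 14 were not in the text available to me, so a relevant listing there cannot be ruled out.
- There is no formal safety test, and section 10.3.1 makes investigator-reported relationship the principal consideration.

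All of this stands, and it makes the gap narrow. It does not close it. Traces and listings are not a count by treatment. Appendix 4 also pulls both ways for SSc: an exacerbation of a pre-existing condition is an AE, while expected progression of the disease under study is not. Capture therefore rests on the investigator's judgement, which a display independent of AE status would not.

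**Conclusion.** The point holds in limited form. The protocol commits to a display of disease related events on the Safety Population. The SAP does not provide it and does not record the change. An SSc organ event judged to be expected progression, in a participant excluded from Per Protocol, is counted in neither the AE/SAE tables nor Table 9.19.

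The size is unknown. The shift from 0.302 to 0.218 for one uncounted event, and from 0.456 to 0.247 for three, rests on an assumed number of events and on 15 active participants. That the exclusions relate to worsening disease is plausible but not shown. A reader might go further and conclude that the safety results will look falsely clean. The documents show only that the display is missing and that its nearest substitute uses the wrong population for safety. The change is worth making because it is cheap and meets a stated commitment.

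**What to change.** 1. Define disease related events in SAP section 7. Produce Table 9.19 by treatment on the Safety Population, counting events regardless of AE status, as the display that protocol section 10.3.1 promises. Keep the Per Protocol version as support for the CRISS analysis.
2. Add a row for SSc-attributed deaths from the existing Death CRF. If that form does not record attribution to SSc, show all deaths by treatment with the recorded cause.
3. Footnote that CRISS data are not scheduled at Early Withdrawal, so participants who leave the study may still be missed.
4. Reconcile the Appendix 4 passages on exacerbation, new conditions and expected progression as they apply to SSc.

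The cost is one existing table rerun on another population, one row from collected data, a footnote and a text clarification. I would not add an eCRF field for SSc-related hospitalisation. Amendment 5 (April 2020) says all participants had completed treatment, so the field would need new and largely retrospective collection.

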10.3.2. Other Analyses

PK, pharmacodynamic and biomarker exploratory analyses will be described in the RAP.

The analysis approach for exploratory biomarkers will be:

- Relationships between endpoints, explored graphically and using statistical measures of consistency if data allow.
- Profiles / Trends over time of individual endpoints

- Inference using posterior probabilities of the true within participant change from baseline and true between group treatment difference using non-informative prior distributions.

In addition to the univariate analysis of the change from baseline in each biomarker, a multivariate analysis of endpoints of several biomarkers of fibrosis may also be performed.

The primary between-group analysis will be between the placebo and GSK2330811 groups. However if a difference in baseline levels of key biomarkers of fibrosis is observed by mycophenolate use then an alternative primary comparison will be considered.

The following PK/PD analyses will be conducted if data permit:

- To examine the relationship between plasma concentrations of GSK2330811, and target OSM concentration (total).
- To examine the relationship between plasma concentrations of GSK2330811, and platelet count.

10.3.3. Interim Analyses

In line with routine pharmacovigilance, an internal GSK SRT will review blinded safety data at appropriate intervals during the study conduct. See [Appendix 3](#) for further details.

For the purposes of dose escalation a dose escalation review will occur once the appropriate data from cohort 1 has been collected. This dose escalation review along with the interim analyses outlined below will be conducted by the DRC. The activities of these and how the study integrity will be maintained are included in the DRC charter.

For the purpose of assessing target engagement, an unblinded interim analysis of PD and PK data will occur once an appropriate number of cohort 2 participants have completed the day 57 (Week 8) visit. The baseline total OSM and mean target engagement relative to the modelled predictions will be considered.

An interim analysis may be conducted to assess the baseline variability of key biomarkers once at least 16 participants have been randomised into cohort 2 of the study. This may lead to the adjustment of the biomarker assessment strategy.

An unblinded sample size re-estimation may be conducted once approximately 16 participants from cohort 2 complete the day 85 (Week 12) visit, where the key systemic biomarkers will be reviewed. This may lead to an increase in the sample size up to a maximum of 40 participants.

In addition to the formal planned interim analyses, further data reviews may be carried out by the DRC and/or senior managers not involved in the study conduct to aid in internal decision making. These reviews will have no impact on the conduct of the study.

The RAP will describe the planned interim analyses in greater detail.

12. APPENDICES

12.1. Appendix 1: Abbreviations and Trademarks

Abbreviations

ACE	Angiotensin Converting Enzyme
ADA	Anti-drug Antibody
AE	Adverse Event
ALT	Alanine Aminotransferase
APTT	Activated Partial Thromboplastin Time
AR	Angiotensin II Receptor
AST	Aspartate Aminotransferase
AUC	Area Under Concentration-Time Curve
CI	Confidence Interval
CONSORT	Consolidated Standards of Reporting Trials
COVID-19	Coronavirus Disease 2019
CPK	Creatine Phosphokinase
CRF	Case Report Form
CRISS	Composite Response Index in diffuse cutaneous Systemic Sclerosis
CRP	C-Reactive Protein
CTCAE	Common Terminology Criteria for Adverse Events
CV	Cardiovascular
dcSSc	Diffuse Cutaneous Systemic Sclerosis
DLCO	Diffusion Capacity of the Lungs for Carbon Monoxide
DRC	Data Review Committee
ECG	Electrocardiogram
eCRF	Electronic Case Report Form
EDTA	Ethylenediaminetetraacetic Acid
ELF	Enhanced Liver Fibrosis
EMA	European Medicines Agency
FDA	Food and Drug Administration
FSH	Follicle Stimulating Hormone
FTIH	First Time in Human
FVC	Forced Vital Capacity
GCP	Good Clinical Practice
GFR	Glomerular Filtration Rate
GSK	GlaxoSmithKline
HAQ-DI	Health Assessment Questionnaire Disability Index HAQ-DI
HBcAb	Hepatitis B Core Antibody
HBsAg	Hepatitis B Surface Antigen
HDL	High density lipoproteins
HIV	Human Immunodeficiency Virus
hr	Hour(s)
HRT	Hormone Replacement Therapy
IB	Investigator's Brochure

ICF	Informed Consent Form
ICH	International Conference on Harmonization
IDSL	Integrated Data Standards Library
IEC	Independent Ethics Committee
IL-6	Interleukin 6
IP	Investigational Product
INR	International Normalised Ratio
IRB	Institutional Review Board
IV	Intravenous
IWRS	Interactive Web Response System
kg	Kilogram
L	Litre
LDL	Low Density Lipoproteins
LIF	Leukemia Inhibitory Factor
LLN	Lower Limit of Normal
mAb	Monoclonal Antibody
MCH	Mean Corpuscular Haemoglobin
MCHC	Mean Corpuscular Haemoglobin Concentration
MCP-1	Monocyte Chemotactic Protein 1
MCV	Mean Corpuscular Volume
MDRD	Modification of Diet in Renal Disease
MedDRA	Medical Dictionary for Regulatory Activities
mg	Milligrams
mL	Milliliter
mRNA	Messenger Ribonucleic Acid
mRSS	Modified Rodnan Skin Score
msec	Milliseconds
NOAEL	No Observed Adverse Effect Level
OSM	Oncostatin M
OSMR	Oncostatin M Receptor
PD	Pharmacodynamic
PDE5	Phosphodiesterase 5
PhGA	Physician Global Assessment
PK	Pharmacokinetic
POM	Proof of Mechanism
PtGA	Patient Global Assessment
QTc	QT Duration Corrected for Heart Rate
QTcB	QT Duration Corrected for Heart Rate by Bazett's Formula
RAP	Reporting and Analysis Plan
RBC	Red Blood Cell
SAE	Serious Adverse Event(s)
SC	Subcutaneous
SD	Standard Deviation
SHAQ	Scleroderma Health Assessment Questionnaire
SOP	Standard Operating Procedure
SRM	Study Reference Manual

SRT	Safety Review Team
SSc	Systemic Sclerosis
t	Time of last observed quantifiable concentration
TB	Tuberculosis
TE	Target Engagement
TMDD	Target-Mediated Drug Disposition
TNF	Tumor Necrosis Factor
ULN	Upper Limit of Normal
VEGF	Vascular Endothelial Growth Factor
Vss/F	Steady State Volume of Distribution / Bioavailability
vWF	Von Willebrand Factor
WBC	White Blood Cells
WOCBP	Women of Child Bearing Potential

Trademark Information

Trademarks of the GlaxoSmithKline group of companies
NONE

Trademarks not owned by the GlaxoSmithKline group of companies
NONMEM
QuantiFERON-TB Gold
QuantiFERON-TB Gold PLUS
SOMAScan

